### 3.2 Sample Size

The approximate sample size of 320 subjects is chosen to provide approximately 80% power to detect  $\geq 25\%$  absolute improvement for at least 1 efavaleukin alfa dose group

relative to placebo in the primary endpoint of SRI-4 response rate at week 52 at a significance level of 0.025 (1-sided) using a Bayesian Hierarchical Model, assuming a 40% response rate in placebo group.

Because enrollment **was** stopped early, the actual sample size **is** smaller.

### 3.3 Adaptive Design

The prospectively defined adaptive features include RAR, early decision for futility and an early trigger for administrative success. The following adaptations are based on the planned IA results:

- Adaptive randomization begins after a fixed allocation period. After each IA (if before full enrolment), the randomization probability for each of the 3 active doses may be changed based on clinical efficacy after an IA, while the randomization allocation for placebo is kept constant at 25%.
- Efficacy is assessed against predefined early stopping rules for futility from the second IA until before the last IA. If futility is triggered, the study could be terminated, e.g., continued enrollment and IP dosing for previously enrolled subjects would be stopped, etc.
- Efficacy is assessed against predefined rules for early administrative success only at the last planned IA. If administrative success is determined, downstream activities may be planned/initiated, but the execution of the trial would not be stopped or altered.
- All adaptive decisions will be based on the SRI-4 response at week 52 with longitudinal modeling of SRI-4 response data. For a subject who has not yet completed through week 52, their 52-week value will be imputed using a longitudinal model based on their week 16, 20, or 24 SRI-4 response data, whichever is the latest.

Modeling and simulations were used to design this Bayesian adaptive trial and refine study design features to achieve optimal operating characteristics, including but not limited to type I error, power and estimation bias.

The IAs will be conducted by an Independent Biostatistics Group (IBG) and will be reviewed by a Data Monitoring Committee (DMC), both external to Amgen. The study team, investigators and subjects will remain blinded to the results of the IAs unless futility is determined.

**Table 3-1 Planned Analyses Schedule**  
**Decisions at Each Interim Analysis and Final Analysis**

Timepoint	Adaptive Decision	Number of subjects with opportunity to complete week 24
1 st IA	RAR	40
2 nd IA	Futility, RAR	72
3 rd IA	Futility, RAR	104
4 th IA ac	Futility, RAR	136
5 th IA ac	Futility, RAR	168
6 th IA ac	Futility, RAR	200
7 th IA ac	Futility, RAR	232
Last IA bc	Administrative success	320
Final Analysis	Not applicable	All subjects reach EOS

IA = interim analysis; RAR = response adaptive randomization; EOS = end of study

a Interim analyses are planned after every 32 subjects are randomized and have had the opportunity to complete the week 24 assessment until full enrollment or until futility is determined for all doses at an IA. Number of IAs will depend on the observed enrollment rate.

b Last IA is the all-subjects-week-24 IA. The administrative success analysis at the last IA will not result in any adaptive decision for the ongoing study.

c Canceled due to study early termination.

#### 4. Covariates and Subgroups

##### 4.1 Planned Covariates

**Not applicable.**

##### 4.2 Subgroups

The primary endpoint will be **summarized** within each of the subgroups listed below. If the subgroup sample size is less than 10% of the population, this subgroup may not be evaluated. The subgroups of interest include the following:

- baseline hSLEDAI (< 10,  $\geq$  10)
- region (North America + Western Europe + Asia Pacific, ROW)

#### 5. Definitions

##### 5.1 Basic Definition

**Investigational Product (IP)**

Efavaleukin alfa and placebo.

**Enrollment/Randomization Date**

The enrollment/randomization date is the date on which a subject is assigned to a treatment group by the IRT system.

### **First Dose Date**

The first dose date is the date of administration of the first dose of IP; this may or may not be the same as randomization date.

### **Actual Treatment Received**

The actual treatment received is the IP the subject actually received, regardless of what the subject was randomized to. In cases where a subject received both efavaleukin alfa and placebo, the actual treatment received will be the efavaleukin alfa dose. In cases where a subject received multiple different efavaleukin alfa doses, the actual treatment received will be based on the highest efavaleukin alfa dose received. **In cases where the subject received more than [REDACTED] efavaleukin alfa dose, the subject will be assigned to [REDACTED] efavaleukin alfa dose.**

### **Duration of IP exposure**

The duration of IP exposure will be derived as the date of the last IP administration plus 13 days (14-day window-1), end of study date or data cutoff date, whichever occurs first, minus the date of first IP administration plus 1 day.

### **Flare Exposure Time**

The flare exposure time is the time from study day 1 up to the last flare assessment date.

### **Treatment-emergent adverse event**

Treatment-emergent adverse events are **defined as** events categorized as Adverse Events (AEs) starting on or after first dose of IP as determined by “Did event start before first dose of investigational product?” equal to “No” or missing on the Events eCRF and up to the end of study date.

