7.3 Lost to Follow-up

A subject will be considered lost to follow-up if **they** repeatedly fail to return for scheduled visits and is unable to be contacted by the study site.

The following actions must be taken if a subject fails to return to the clinic for a required study visit:

- The site must attempt to contact the subject and reschedule the missed visit as soon as possible and counsel the subject on the importance of maintaining the assigned visit schedule and ascertain whether or not the subject wishes to and/or is able to continue in the study.
- In cases in which the subject is deemed lost to follow-up, the investigator or designee must make every effort to regain contact with the subject (where possible, 3 telephone calls and, if necessary, a certified letter to the subject's last known mailing address or local equivalent methods). These contact attempts are to be documented in the subject's medical record.
- If the subject continues to be unreachable, they will be considered to have withdrawn from the study with a primary reason of lost to follow-up.
- For subjects who are lost to follow-up, the investigator should search publicly available records where permitted to ascertain survival status. This ensures that the data set(s) produced as an outcome of the study is/are as comprehensive as possible.

8. Study Assessments and Procedures

Study procedures and their time points are summarized in the Schedules of Activities (see [Table 1-2](#), [Table 1-3](#), and [Table 1-4](#)).

If an enrolled subject is subsequently determined to be ineligible for the study, this must be discussed with the sponsor immediately upon occurrence or awareness to determine if the subject is to continue or discontinue study treatment.

Adherence to the study design requirements, including those specified in the Schedule of Activities, is essential and required for study conduct.

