8.3.4.1.2 Serious Adverse Events

The investigator is responsible for ensuring that all serious adverse events observed by the investigator or reported by the subject that occur after signing of the informed consent through 6 weeks (+5 days) after the last dose of the investigational product/end of study/safety follow-up visit, whichever occurs later, are reported using the Events eCRF.

All serious adverse events will be collected, recorded and reported to the sponsor or designee immediately and no later than 24 hours of the investigator's awareness of the event, as indicated in Section 11.4. The investigator will submit any updated serious adverse event data to the sponsor immediately and no later than 24 hours of it being available.

Since the criteria in the CTCAE grading scale differs from the regulatory criteria for serious adverse events, if adverse events correspond to grade 4 CTCAE toxicity grading scale criteria (eg, laboratory abnormality reported as grade 4 without manifestation of life-threatening status), it will be left to the investigator's judgment to also report these abnormalities as serious adverse events. For any adverse event that applies to this situation, comprehensive documentation of the event's severity must be recorded in the subject medical records.

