#### End of Study Date

End of study for each subject is the date recorded on the End of Study CRF page.

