#### Final Analysis Period

The time period from study day 1 to the end of study date, inclusive.

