## **9.6 Safety Analyses**

In the safety analysis, data up to the end of study will be summarized in the final analysis.

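### For the few subjects who leave the study within 6 weeks of a dose, the SAP's end-of-study cut can leave out serious adverse events that the protocol collects

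*SAP*

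**What the plan says.** **SAP.** Section 5.1 closes the treatment-emergent window with the words "missing on the Events eCRF and up to the end of study date". Section 5.3 makes that date subject-specific: "End of study for each subject is the date recorded on the End of Study CRF page". Section 5.4 defines the final analysis period as "The time period from study day 1 to the end of study date, inclusive". Section 9.6 says "In the safety analysis, data up to the end of study will be summarized" in the final analysis. Section 9.6.1 then lists summaries of treatment-emergent, serious and fatal adverse events.

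**Protocol.** Section 8.3.4.1.2 requires serious events on the Events eCRF from consent "through 6 weeks (+5 days) after the last dose of the investigational product/end of study/safety follow-up visit, whichever occurs later". Section 8.3.4.1.1 collects adverse events in general only from first dose through end of study.

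**How subjects leave.** Section 8.1.2 asks anyone leaving the study before week 52 to complete an early termination visit, timed to give at least 6 weeks of safety data after the last dose. Section 8.1.3 provides a week 56 visit for completers who need it. SAP Section 3.1 says that subjects stopped for futility were followed 6 weeks after last dose before they left. Section 7.2.1 also lists consent withdrawal and loss to follow-up as reasons for leaving. For lost subjects, Section 7.3 says that "the investigator should search publicly available records where permitted to ascertain survival status". Section 7.2 allows publicly available data to be used after consent withdrawal where that is permitted.

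**The concern.** The protocol sets its serious-event window by whichever date comes last. That wording provides for last dose plus 6 weeks falling after a subject's end of study. The SAP's cut makes no such provision, and SAP Section 10 does not list the difference among the changes from protocol-specified analyses.

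The subjects exposed to the gap have been dosed recently and have left without the 6-week visit. A serious event in that interval may still be drug-related. Serious and fatal events are rare, so one omission can alter a table. The final analysis is descriptive, so nothing later in the analysis would correct it.

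**Working it through.** **1. The planned route.** The final dose is at week 50, which is study day 1 + 7 × 50 = 351. Adding 6 weeks gives 351 + 42 = 393, and (393 − 1)/7 = 56 weeks. This reproduces the protocol's 56-week subject duration and the SAP's week 56 target day of 393. A completer's end of study therefore falls at about last dose plus 6 weeks, and the two windows meet.

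**2. Days uncounted.** Let d be the days from last dose to the recorded end of study date. The protocol window runs W = 42 days after last dose, or 42 + 5 = 47 with the tolerance. I read Section 8.3.4.1.2 as offering three candidate end dates, of which the latest applies. Uncounted days = max(0, W − d).

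| d (days) | W = 42 | W = 47 |
|---|---|---|
| 0 | 42 | 47 |
| 14 | 28 | 33 |
| 28 | 14 | 19 |
| 42 | 0 | 5 |
| 47 | 0 | 0 |

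**3. Which subjects have d below 42?**
- Week 56 follow-up, early termination visit as scheduled, or futility termination: d is about 42 or more, so the loss is 0 to 5 days.
- Stopping investigational product but staying in the study: end of study is not triggered, because Sections 7.1 and 8.1.2 keep these subjects under assessment.
- Consent withdrawal or loss to follow-up: d can be below 42. This is the affected group.

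**4. Which events?** Only serious and fatal ones. Non-serious events are collected through end of study, which matches the SAP. The SAP cut is on event start, so an event that begins by the end of study date and later proves fatal is still counted.

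**5. Size.** The documents give neither the number of early leavers nor a serious-event rate, so these inputs are assumptions. Expected uncounted events = N × share leaving within 6 weeks of last dose × mean gap/365.25 × events per person-year.

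| Share | Gap (days) | Rate per person-year | N = 104 | N = 320 |
|---|---|---|---|---|
| 2% | 14 | 0.05 | 0.004 | 0.012 |
| 5% | 28 | 0.15 | 0.06 | 0.18 |
| 10% | 47 | 0.30 | 0.40 | 1.24 |

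For the last row at N = 104: 104 × 0.10 × 47/365.25 × 0.30 = 0.40.

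Here 104 is the number of subjects with the opportunity to complete week 24 at the third interim analysis, so it is a lower bound on enrolment. The planned total of 320 was not reached (SAP Section 3.2). The formula also treats every event in the gap as collected, which overstates the loss.

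**The case against.** The strongest reply is that the protocol closes most of this gap. It requires at least 6 weeks of safety follow-up for all subjects, times the early termination visit accordingly, and leaves the treatment-emergent definition to the SAP. That stands. A reader might infer from the two definitions that serious events soon after any dropout are lost. The documents do not support this, because most routes out of treatment or the study carry the 6-week follow-up. The early termination visit cannot be enforced on someone who is lost or has withdrawn consent, so a residual group remains.

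Ascertainment in that group is poor. After consent withdrawal only public data may be used, where permitted. For lost subjects the protocol seeks only survival status. The serious-event form also asks for the cause of a fatal event and does not accept death itself as an entry. This stands too. Such events are possible, but few would reach the eCRF.

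A reader might also infer that these events fall outside every safety table. That depends on reading the end of study in SAP Section 9.6 as each subject's own date. Sections 5.3 and 5.4 make this reasonable, but Section 9.6 does not say so, and protocol Section 4.4 also defines an end of study for the whole trial. On the whole-trial reading, the serious and fatal summaries could keep these events while the treatment-emergent tables drop them. The two sets of tables would then have different windows, which also needs a clarifying sentence. Separately, related serious events reported after the study ends still enter the sponsor's safety database (protocol Section 8.3.4.1.3).

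**Conclusion.** The mismatch is real but narrow. For a subject who withdraws consent or is lost within 6 weeks of a dose, a serious or fatal event that starts after the recorded end of study date can be reportable under the protocol and excluded by SAP Section 5.1. The interval is at most 42 to 47 days per such subject, and 0 to 5 days for everyone else.

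The number affected is unknown. Under the assumed ranges, less than half an event is expected per 104 subjects, and about one at the extreme assumptions with the full 320, which was not reached. A single missed event in an arm of 26 (104/4) would be 1/26 = 3.8 percentage points. That only illustrates what one event would do: actual arm sizes are not given, and allocation could become unequal under adaptive randomization. Nothing in the documents shows that early exit differs by arm, so a bias between arms cannot be claimed.

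With no treatment comparisons in the final analysis, the practical effect is low. The point is worth settling because the rule as written excludes events that the protocol asks for, and the correction is nearly free.

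**What to change.** For serious and fatal adverse events only, change the cut in SAP Sections 5.1 and 9.6 to match protocol Section 8.3.4.1.2: the later of the subject's end of study date and last dose + 6 weeks (+5 days). Alternatively, keep the present cut and add a separate table or listing of serious and fatal events with onset after the end of study date. In either case, state in Section 9.6 whether end of study means the subject's date or the trial's.

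Include deaths found in public records only where permitted, as protocol Sections 7.2 and 7.3 require. Keep the end of study cut for non-serious events. They are collected only to that point, so extending the whole treatment-emergent window would mix two ascertainment periods in one incidence figure.

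The cost is one or two sentences and no new data collection. Serious-event figures may become slightly less favourable. Under the first option, serious and non-serious events would have different cut dates, which needs a table footnote.

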### **Baseline medication**

Baseline medication is defined as any medication with start date on or before study day 1 and ongoing while on study.

### **Concomitant medication**

Concomitant medication is defined as any medication with start date prior to study day 1 and ongoing while on study or any medication with start date on or after study day 1 and up to the end of study.

### **Prednisone-equivalent dose**

The prednisone-equivalent dose of OCS will be computed based on the table below. Additionally, a multiplier will be applied depending on the dosing frequency: 2 for 'twice daily' or 'every 12 hours' and 0.5 for every other day. For example, cortisone 25 mg is equivalent to prednisone 5 mg and a cortisone 25 mg twice daily is equivalent to prednisone 10 mg/day.

Corticosteroids	Equivalent dose
Prednisone	5 mg
Betamethasone	0.75 mg
Cortisone	25 mg
Deflazacort	6 mg
Dexamethasone	0.75 mg
Hydrocortisone	20 mg
Methylprednisolone/Meprednisone/ Methylprednisolone Acetate	4 mg
Prednisolone	5 mg
Triamcinolone	4 mg

## **5.2 Study Points of Reference**

### **Baseline**

Baseline is the last measurement for the endpoint of interest taken before the first dose of IP. If the measurement is taken on the same day as the first dose and the exact measurement time relative to the first dose is unknown, it will be assumed to have been taken prior to the first dose of IP. If a subject did not receive IP, baseline is the closest recorded measurement on or prior to the randomization date.

### **Study Day 1**

Study day 1 for each subject is the first day of IP administration or the day of randomization for subjects who did not receive IP.

### **Study Day**

Study day for each subject is defined as (day of interest – study day 1) + 1 for dates on or after study day 1, or (day of interest – study day 1) for dates prior to study day 1.

### 5.3 Study Dates

#### End of 52-Week Treatment Period Date

End of 52-week treatment period date for each subject is defined as the date of the last assessment for the week 52 visit, the end of study date in case of **subject** early termination, study day 394 or [REDACTED] (date of study early termination), whichever occurs first.

#### End of Study Date

End of study for each subject is the date recorded on the End of Study CRF page.

### 5.4 Study Time Intervals

#### Treatment Period

The time period from study day 1 to the end of treatment period date inclusive.

#### Final Analysis Period

The time period from study day 1 to the end of study date, inclusive.

### 5.5 Arithmetic Calculations

#### Change from baseline

The arithmetic difference between a post-baseline value and baseline for a given timepoint:

(post-baseline value – baseline value).

#### Percent change from baseline

The change from baseline divided by baseline value and multiplied by 100:

(change from baseline / baseline) \* 100.

**If the change from baseline is not equal to zero and the baseline value is zero then percent change from baseline is not defined. If the change from baseline is equal to zero and the baseline value is also zero then percent change from baseline is 100.**

#### Fold change from baseline or ratio from baseline

Fold change from Baseline equals the post-baseline value divided by the baseline value. If the change from baseline is not equal to 0 and the baseline value is 0 then fold change

is not defined. If the change from baseline is equal to 0 and the baseline value is also 0 then fold change is 1.

## 5.6 Efficacy Assessments

### Hybrid Systemic Lupus Erythematosus Disease Activity Index (hSLEDAI)

The hSLEDAI is a global index that evaluates disease activity and includes both laboratory and clinical parameters and consists of 24 items. The maximum score is 105. Hybrid SLEDAI is the index score used during the validation of the SLE Responder Index (SRI) (Navarra et al, 2011; Furie et al, 2011). The hSLEDAI includes scleritis and episcleritis in visual disturbance assessments. Scleritis and episcleritis should be confirmed by ophthalmologist and clinically stable if used for scoring purposes. Additionally, arthritis should be scored when > 2 joints manifest signs of inflammation strictly defined as the presence of tenderness plus one of the following: swelling, effusion, warmth or erythema. The presence of tenderness alone is not sufficient and at least 3 joints, and not only 2, must be affected. In this study, for arthritis to be scored it is required to involve the small joints of hands and/or wrists.

Findings should reflect activity during the 30 calendar days prior to the current visit. Details of hSLEDAI descriptors and the scoring algorithm are described in [Appendix B](#).

### British-Isles Lupus Assessment Group (BILAG)

The BILAG index (BILAG 2004) evaluates disease activity in 9 separate organ systems and comprises a total of 97 items. Each item is measured qualitatively by review of medical history and physical examination (yes/no, improving/same/worse/new) or quantitatively by measuring laboratory values. Based on these items, each of the 9 organ systems allocated an alphabetical score of A (most active), B (moderate activity), C (minor activity), D (stable) or E (never present). The BILAG index can be converted into a numerical score (A grade = 12 points, B = 8, C = 1, D = 0, E = 0). Findings should reflect activity during the 4-week period prior to the current visit and should be related to the subject's SLE. Details of BILAG descriptors and the scoring algorithm are described in [Appendix B](#).

### Physician Global Assessment (PGA) – Visual Analog Scale

The PGA is a visual analog scale (VAS) using 4 descriptive anchors for assessing disease activity over the last 4 weeks. When scoring the PGA VAS, the previous visit score should be noted, and the current score should be relative to that previous visit. The score ranges from 0 to 3 with 3 indicating severe disease. This refers to the most

severe possible disease and does not reflect the most severe ever seen in a particular subject, but the most severe disease ever seen in all SLE patients.

This is a global assessment, factoring in all aspects of the subject's lupus disease activity. It should not reflect non-lupus medical conditions. An increase of  $\geq 0.3$  points ( $> 10\%$  on the 3 point-VAS) from baseline is considered clinically significant worsening of disease.

